Several studies dealt with the question of differentiating between benign and malignant processes of the pancreas using 18F-FDG PET/CT imaging. However, a reliable statement can currently only be made by histopathological assessment (considered the gold standard). For this reason, a priori no conclusion can currently be drawn as to the malignancy or benignity of the lesion in question. According to recent studies, malignant pancreatic diseases occur in patients with suspected pancreatic carcinoma and condition after pancreateoduodenectomy or fine needle aspiration with a frequency of 66-81% (47-78% of which are adenocarcinomas), benign diseases with a frequency of 19-34%, of which about 60% are inflammatory diseases and 40% benign cystic tumors [2-5].

In this study, patients with suspected benign diseases that are not operated and do not have a fine needle biopsy and are only monitored by radiological follow-ups are excluded.

According to the current status of science, there are no studies in the literature concerning the characterization of pancreatic lesion expansions using the "Time-of-Flight"-technique (TOF) in the framework of PET/CT. The TOF technique is a new reconstruction algorithm in PET/CT that can only be applied to newer devices. High-definition PET technology can significantly improve spatial resolution (to 2 mm) and increase sensitivity (TOF) by a factor of 3. The combination of both techniques (HD-PET with TOF) is called Ultra HD-PET.

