In the area of pancreatic lesions, it is difficult to distinguish adjacent anatomical structures (duodenum). For this reason, in the present study additionally, a parenteral iodine-containing (Visipaque®) and a negative oral contrast medium (500 ml water) will be administered. One difficulty of such studies is that the dignity of the tumor can only be determined after histopathological examination of the surgical specimen.

Study hypothesis

Early- (30min p.i.) and delayed images (90min p.i.), diagnostic CT of the abdomen with contrast medium and Time-of-Flight (TOF)-reconstruction within the framework of 18F-FDG PET/CT allow an improvement in the differentiation of malignant from benign lesion expansions of the pancreas.

Aim of the study

[figure not shown]
The aim of the study is to improve the differentiation between malignant and benign lesions in the pancreas in patients with suspected pancreatic cancer by images 30min und 90min p.i. and a diagnostic CT of the abdomen with contrast medium in the context of TOF-18F-FDG PET/CT and thus to improve the quality of PET/CT findings. Also, a cut-off value of SUV will be determined in correlation with the histopathological results to better differentiate between malignant and benign lesions of the pancreas.

Study process

Assignment with suspected diagnosis

Legend:

- grey: routine examination
- blue: study-specific work steps

Patients

118 patients are to be diagnosed continuously according to protocol.

Inclusion criteria:

- patients with suspected pancreatic cancer (morphologically suspect)
- operation/fine needle puncture

PET/CT examination with TOF-reconstruction algorithm and contrast medium:

- sober
- plasma glucose level < 140 mg/dl
- position capability
- checking of:
 - creatinine value < 1.2 mg/dl (for values >1.2 mg/dl
no administration of contrast medium) and eGFR-value > 45 ml/min/1.73 m²
(for values < 45 ml/min/1.73 m² no administration of contrast medium)
 - TSH-value 0.1-4.0 µU/ml (for values <0.1 µU/ml
no administration of contrast medium)

Exclusion criteria:

- patients under 18 years
- plasma glucose level > 140 mg/dl
- patients with histopathologically confirmed distant metastases at the time of PET/CT examination
- patients with non-pancreatic tumors
- patients, who **will not undergo surgery** or had **no fine needle puncture (FNP)** and therefore have no histopathological findings of the pancreas
- pregnancy

Patient recruitment

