The study is a prospective single-center clinical trial with one arm. During this clinical study at intervals of 4 weeks, the following examinations will be performed: PET/CT-examination, surgery or fine needle puncture. If the patients do not have a fine needle puncture or surgery, they are automatically excluded from the study due to missing histopathological findings. The study design is shown in Figure 1 below.

Figure 1 Flowchart of screening and inclusion process

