2.1 Sample size planning

One hundred eighteen patients would be required to demonstrate an improvement in specificity of 25% (to 70%) with the new method assuming a specificity of the current method of 45% at a prevalence of malignant lesions of 70% (corresponding to 30% benign lesions). The calculation of these values is based on a formula that selects the sample size so that the lower limit of the 95% confidence interval by the expected specificity of the new method most probably exceeds the specificity value of the current method, i.e., the confidence interval no longer contains this value. With a power of (in this case) 90%, you can say that the specificity of the new method is higher than the old one.

3. Aims and objectives

The aim of the study is to analyze if 30 and 90min p.i. images and a diagnostic CT of the abdomen in the context of TOF-18F-FDG-PET/CT can improve the differentiation between malignant and benign lesions in the pancreas in patients with suspected pancreatic cancer.

4. Outcomes

This section will present the outcomes investigated to answer the study aims and objects. The analyses are described in section 6 Analyses.

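### The 90% power in SAP 2.1 is the nominal value of a planning formula; the two-sided confidence-interval rule it is attached to has about 81–87% power with 118 verified patients at 30% benign

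*SAP*

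**What the plan says.** SAP 2.1 gives the size and the effect: "One hundred eighteen patients would be required to demonstrate an improvement in specificity of 25% (to 70%) with the new method". The comparator is a fixed value, "assuming a specificity of the current method of 45" per cent, and 70% of lesions are taken to be malignant, 30% benign. The number is attributed to an unnamed formula. It is meant to make it very likely that the 95% interval around the expected specificity lies wholly above the comparator. The section then states: "With a power of (in this case) 90%, you can say that the specificity of the new method is higher than the old one". Neither the type of interval nor its sidedness is named.

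The Protocol, under Patients, repeats the number: "118 patients are to be diagnosed continuously according to protocol". SAP section 2 says of patients without surgery or fine needle puncture that "they are automatically excluded from the study due to missing histopathological findings". No expected rate for this and no allowance for it is given in either document.

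The Protocol's Background information reports malignant disease "with a frequency of 66-81" per cent, hence benign disease in 19–34%.

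**The concern.** Specificity is estimated in benign patients only, so the calculation rests on about 35 people, not 118. At that size three things separate a formula's nominal power from the power of the rule: the normal approximation, the discreteness of the binomial count, and the fact that the number of benign patients is itself random. SAP 2.1 nevertheless gives 90% without qualification, as the chance that the interval will clear 45%.

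A reader of an inconclusive result would assume a 10% chance of missing a true specificity of 70%, when that chance is larger. The benign share matters as well, because the Protocol's own literature range reaches down to 19% while the SAP shows one value only.

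**Working it through.** **Inputs.** From SAP 2.1: comparator p0 = 0.45, expected p1 = 0.70, benign share 0.30, N = 118, 95% interval, power 90%. From the Protocol, Background information: benign share 19–34%. Assumed here: a two-sided interval, and loss rates of 10% and 20% for illustration.

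**1. The plan's figure.** Wald formula with the variance at p1:

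- benign n = (1.96 + 1.2816)² × 0.70 × 0.30 / 0.25² = 35.3
- N = 35.3 / 0.30 = 117.7, rounded up to 118
- nominal power at 118 × 0.30 = 35.4 benign: Φ(0.25 × √(35.4/0.21) − 1.96) = 90.1%

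The stated pair is reproduced.

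**2. Sidedness.** The same formula with a one-sided 95% limit (1.645 in place of 1.96) gives 28.8 benign, rounded up to 29, and 29 / 0.30 = 96.7, so 97 patients. Only the two-sided multiplier leads to 118.

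**3. The rule at a fixed benign count.** With 35 benign, 21 correct gives a Wald lower limit of 0.600 − 1.96 × √(0.600 × 0.400/35) = 0.438, which fails. 22 correct gives 0.629 − 1.96 × √(0.629 × 0.371/35) = 0.468, which passes. Power is therefore P(X ≥ 22), X ~ Bin(35, 0.70), = 86.5%. Repeating this for neighbouring counts and other intervals:

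| Benign patients | Wald | Wilson | Exact (Clopper–Pearson) |
|---|---|---|---|
| 34 | 89.0% | 89.0% | 80.7% |
| 35 | 86.5% | 86.5% | 77.3% |
| 36 | 90.8% | 83.7% | 83.7% |

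The one entry above 90% (Wald, 36 benign) carries a one-sided error of 3.8%, against the nominal 2.5%.

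**4. The rule with a random benign count.** Power = Σ over n of P(n) × P(lower limit > 0.45 | n), with n ~ Bin(N, benign share) and correct calls ~ Bin(n, 0.70):

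| Verified patients, benign share | Wald | Wilson | Exact |
|---|---|---|---|
| 118, 30% | 86.7% | 86.0% | 81.4% |
| 118, 19% | 70% | 67% | 59% |
| 118, 34% | 90.2% | 89.8% | 86.3% |
| 106 (assumed 10% loss), 30% | 83% | 82% | 77% |
| 94 (assumed 20% loss), 30% | 79% | 77% | 71% |

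At 19% benign (118 × 0.19 = 22.4 patients) the plan's own formula gives only Φ(0.25 × √(22.4/0.21) − 1.96) = 73%.

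**The case against.** The strongest reply is that nothing was miscalculated. The SAP describes a formula built on the interval around the expected specificity, that formula gives 118, and its nominal power is 90.1%. This stands. A reader might infer an arithmetic error from the gap, and the documents do not support that; the gap comes from the approximation, the discreteness and the random benign count.

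Second, the SAP leaves the interval open. With a one-sided 95% limit, average power would be 91.9% (Wald), 91.5% (Wilson) or 88.3% (exact). This does not rescue the figure, since a one-sided limit in the same formula would have led to 97 patients. The SAP also describes the interval as no longer containing the comparator, which is ordinary two-sided language. It does stand that the lowest figure, 81.4%, needs an exact interval the SAP never mentions; under the Wald interval that matches its formula the shortfall is about 3 points.

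Third, a reader might infer that 118 is the number scanned, with unverified patients then removed. That is not established. The Protocol lists operation or fine needle puncture among the inclusion criteria, so 118 may already mean verified patients. The wording is ambiguous, and the loss rates above are illustrations only.

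Fourth, SAP 6.1 plans ROC analysis, DeLong comparisons and calculated sensitivity and specificity, but no test of specificity against 45%. The 90% therefore governs no analysis in section 6. This limits the severity, although the figure remains the only justification given for the size of the trial.

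**Conclusion.** The point holds as a misdescription of power. Given SAP 2.1's own assumptions, a two-sided 95% interval and 118 histologically verified patients, the stated rule has average power of 86.7% (Wald), 86.0% (Wilson) or 81.4% (exact). The shortfall is 3 to 4 points under Wald or Wilson and about 9 under the exact interval; the chance of missing a true specificity of 70% is 13–19%, not 10%.

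The benign share matters more than the choice of interval. At the favourable end of the Protocol's range 90% is essentially met with Wald or Wilson; at the unfavourable end power is 59–70%. The effect of missing histology cannot be sized from the documents.

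Severity is moderate. It would go too far to conclude that the trial must enrol more patients.

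**What to change.** In SAP 2.1:

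- Describe 90% as the nominal power of the Wald planning formula with the variance at 70%.
- Name the interval and its sidedness. With a two-sided 95% Wilson interval, state power of about 86% for 118 histologically verified patients at 30% benign; with the exact interval, 81%.
- Give the range for 19–34% benign: 67% to 90% with Wilson, 59% to 86% with the exact interval.
- State whether 118 counts patients before or after exclusion for missing histology. If before, give the power for the number expected to remain.

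The change is to wording only: no extra enrolment and no change to the analyses in section 6. The cost is a slightly less favourable stated power.

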4.1 Primary outcome

SUVmax at 30 and 90 min p.i. in the PET/CT images with and without TOF over the pancreatic lesion.

4.2 Secondary outcome

Better demarcation of pancreatic lesions of the adjacent anatomical structures as well as the tumor size in cm.

4.3 Safety outcomes

Adverse events

Possible adverse events are reported in the case report form.

Concomitant medications

Usage of diabetes or thyroid medications before PET/CT examination will be recorded.

5. Populations to be analyzed

There is only one population in this clinical trial. All patients undergo a TOF-18F-FDG PET/CT examination with images 30 and 90min p.i. with a diagnostic CT of the abdomen. In all patients exist PET images with and without TOF.

6. Analyses

All outcomes will be presented using ROC-analysis or descriptive statistics. SPSS version 25 and R will be used for all statistical analysis.

6.1 Primary outcome

The primary analysis will compare the SUVmax values of all detected pancreatic lesions in the PET/CT images 30 and 90min p.i. with and without TOF using ROC-analysis. AUC values with and without TOF 30 and 90min p.i. will be compared using the DeLong-test. Sensitivity and specificity of SUVmax of each imaging modality (with and without TOF) in correlation with the

histopathological results will be calculated. Furthermore, a cut-off value of SUVmax for differentiating malignant and benign pancreatic lesions will be computed using ROC-analysis. Besides, sensitivity, specificity, diagnostic accuracy and the positive and negative predictive value of the results of the PET/CT findings in correlation with the histopathological results will be calculated.

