The 18F-FDG PET/CT is indicated for staging in patients with suspected pancreatic carcinoma and was also classified as 1a indication for differentiation between inflammation and pancreatic carcinoma according to the 3rd German Interdisciplinary Consensus [6]. In patients with suspected pancreatic carcinoma, diagnosis is often only possible with difficulty due to the limited anatomical assignment of small focal lesions and discreetly increased tracer-uptake, differentiation between benign and malignant is often not possible, i.e., differentiation between chronic pancreatitis and a malignant process is often only possible to a minimal extent. According to clinical studies [7;8;21-26], the TOF-technique and additional i.v. administration of iodine-containing contrast medium and oral administration of a negative contrast medium can significantly improve the sensitivity and anatomical differentiation of the target organ from adjacent structures. However, this technique has not yet been used in patients with suspected pancreatic cancer.

Another already established method to better distinguish inflammatory from malignant lesions in PET/CT is to take images at two different time points and to compare the Standard Uptake Value (SUV), a measure of regional accumulation intensity, at these two times [3;17;18]. Here an increased FDG-uptake already in the early images is classified as benign/inflammatory, and an increase in FDG -

uptake in the delayed images is classified as malignant. A missing FDG uptake both in the early and the delayed images is considered benign.

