6.2 Secondary outcome

The number of patients with increased tracer-uptake over the pancreatic lesion with and without TOF, and thus the better demarcation of pancreatic lesions of the adjacent anatomical structures will be compared using the McNemar test. Also, differences between the SUVmax values with and without TOF will be compared using the t-test. Furthermore, the mean tumor size including the standard deviation will be calculated.

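### SAP 6.1 restricts the primary ROC and DeLong analysis to detected lesions without defining detection or the unit of analysis; one index lesion per patient, located independently of uptake, would settle both

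*SAP*

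**What the plan says.** The primary analysis in SAP 6.1 begins: "The primary analysis will compare the SUVmax values of all detected pancreatic lesions in the PET/CT images". The next step is "AUC values with and without TOF 30 and 90min p.i. will be compared using the DeLong-test". Sensitivity, specificity and an SUVmax cut-off against histology follow from the same ROC work. Section 6.1 does not define detection, give a rule for lesions without uptake, fix a number of lesions per patient, or name a method for clustered data.

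Five other places bear on the analysis set:

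- SAP 4.1 defines the primary outcome as "SUVmax at 30 and 90 min p.i. in the PET/CT images with and without TOF over the pancreatic lesion": one lesion, with no detection condition.
- SAP 6.2 compares by McNemar test "The number of patients with increased tracer-uptake over the pancreatic lesion with and without TOF". This is again one lesion per patient, and uptake status may differ between reconstructions.
- SAP section 5 says "There is only one population in this clinical trial" and "In all patients exist PET images with and without TOF".
- The protocol's Background information gives the reading rule "A missing FDG uptake both in the early and the delayed images is considered benign".
- The protocol's inclusion criteria admit patients on morphological suspicion, so a lesion need not take up FDG for the patient to enter.

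The sample size in SAP 2.1 is 118 patients, not lesions.

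**The concern.** Under the protocol's own reading rule, a lesion without uptake is a negative test result and not a missing one. If *detected* is applied as visible FDG uptake, the ROC set is selected on the result of the test being evaluated. True negatives and false negatives leave the analysis. Apparent specificity falls, apparent sensitivity rises, the SUVmax cut-off shifts, and the benign group, already the smaller one, shrinks.

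Two further risks follow from the same phrase. If detection is judged separately on each image set, the TOF and non-TOF curves could rest on different lesions, and the paired DeLong comparison would not be fully paired. If *all detected lesions* lets a patient contribute two or more, the units are no longer independent, as the standard DeLong variance requires.

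Both the AUC comparison and the SUVmax cut-off, which is a stated aim of the study, rest on this set.

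**Working it through.** **Planned numbers.** SAP 2.1 gives specificity 70% against 45%, 30% benign lesions, a 95% confidence interval and 90% power. With the variance taken at the expected specificity:

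- Benign lesions needed = (1.960 + 1.282)² × 0.70 × 0.30 / 0.25² = 35.3.
- Patients needed = 35.3 / 0.30 = 117.7, rounded up to 118.

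The stated figure reproduces. It counts one result per patient, about 35 benign and 83 malignant.

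**Leaving out test-negatives.** Specificity 70% is from SAP 2.1. Sensitivity 90% and the share *d* of test-negatives left out are assumptions; the documents give neither. The cut-off is held fixed.

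- Benign: 35 × 0.70 = 24.5 true negatives and 10.5 false positives.
- Malignant: 83 × 0.90 = 74.7 true positives and 8.3 false negatives.
- Apparent specificity = 24.5(1 − d) / [24.5(1 − d) + 10.5].
- Apparent sensitivity = 74.7 / [74.7 + 8.3(1 − d)].

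| Share left out, d | Benign left | Apparent specificity | Apparent sensitivity |
|---|---|---|---|
| 0 | 35 | 70% | 90% |
| 0.25 | 18.4 + 10.5 = 28.9 | 18.4/28.9 = 64% | 74.7/80.9 = 92% |
| 0.50 | 12.25 + 10.5 = 22.75 | 12.25/22.75 = 54% | 74.7/78.85 = 95% |

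**Effect on the AUC, with no cut-off involved.** Suppose SUVmax, on a suitable scale, is normal with unit variance in both groups and means 1.2 apart. The AUC is then Φ(1.2/√2) = 0.80. If every lesion below the 20th percentile of the benign group is left out, about 2% of malignant lesions go as well, and the AUC among the rest is about 0.77. With 10% or 30% of benign lesions left out it is about 0.79 or 0.76. This model too is an assumption.

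**More than one lesion per patient.** Assume 20% of patients have two lesions and a within-patient correlation of 0.5.

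- Per patient, Σm = 0.8 × 1 + 0.2 × 2 = 1.2 and Σm² = 0.8 × 1 + 0.2 × 4 = 1.6.
- Design effect = 1 + 0.5 × (1.6/1.2 − 1) = 1.17.
- The true variance is about 17% above the naive one; equivalently, the naive variance is 1 − 1/1.17 = 14% too low.

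This design effect is the one for a mean, so it is only a rough guide for a difference between paired AUCs.

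**The case against.** The strongest reply is that *detected* need not mean FDG-avid. SAP 6.1 refers to PET/CT images, and the examination includes a two-phase contrast CT intended to delineate the pancreas. A mass seen on CT without uptake is then detected and still has a measurable SUVmax. SAP 4.1 attaches no detection condition. The McNemar comparison in 6.2 needs non-avid cases to be kept, and the protocol's reading rule classifies such lesions rather than discarding them. This stands: on that reading the selection bias does not arise. But 6.1 is the operative text for the primary analysis, and it does not say which reading applies.

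A reader might infer three stronger things that the documents do not support.

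- *That the TOF and non-TOF curves will rest on different lesions.* Section 6.2 allows uptake status to differ between reconstructions. It does not say that a lesion leaves one of the curves, and SAP section 5 secures both reconstructions for every patient.
- *That the DeLong test is invalid as planned.* No passage says that any patient contributes more than one lesion, and 4.1 and 6.2 point to one. With one lesion per patient the test is sound.
- *That the trial loses its planned power for specificity.* SAP 2.1 attaches the 70% to the new method and does not tie it to the SUVmax ROC. Section 6.1 also plans sensitivity and specificity of the PET/CT findings separately, without the restriction to detected lesions.

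It is also fair to object that the table holds the cut-off fixed, whereas 6.1 derives it from the data. The table shows the direction and order of the effect, not the values the analysis would report.

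**Conclusion.** The point holds as a conditional one. The lesion set stated in 6.1 for the primary analysis is undefined and does not agree with 4.1, 6.2 or a sample size counted in patients.

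If detection is taken as PET uptake, the ROC is conditioned on the test result. Under the assumptions shown, leaving out a quarter of the test-negatives moves specificity from 70% to 64% and sensitivity from 90% to 92%, with 29 benign lesions left. If detection includes the CT part, none of this occurs. The clustering problem exists only if some patients contribute several lesions. The sample size itself is not in question here.

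The change should be made, because the plan can exclude all three risks at almost no cost. Confidence is medium, since the size depends on shares that the documents do not give.

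**What to change.** In SAP 6.1, replace the set of all detected lesions with the following:

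- One index lesion per patient: the morphologically suspect lesion with histology, located by a rule that does not depend on FDG uptake.
- SUVmax measured at that site on all four image sets (30 and 90 min, with and without TOF), whether or not uptake is visible.
- ROC and DeLong analyses run on these patient-level values, so that every curve uses the same patients.
- Further lesions used only in a supportive analysis that clusters by patient.

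The cost is one paragraph in an SAP still marked as a draft, plus SUVmax measurements at non-avid sites on images that already exist. No new patients or scans are needed. Where no contrast medium was given, the location rule should say which images define the site. The downside is that additional lesions no longer enter the primary analysis.

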Statistical Analysis Plan (SAP)

Evaluation of the diagnostic value of TOF-18F-FDG PET/CT in patients with suspected pancreatic cancer

Principal Investigator	[name] Specialist in Nuclear Medicine Medical University of Graz Department of Radiology, Division of Nuclear Medicine
Protocol Identification Number	Protocol TOF-P V1 (dated 2013-09-25)
Document Date	31.03.2019
Version	Draft 0.1

Abbreviations

AUC	Area under the curve
CT	Computed tomography
FDG	Fluorodeoxyglucose
p.i.	post injectionem
PET/CT	Positron emission tomography/computed tomography
ROC	Receiver operating characteristic
SUVmax	Maximum Standard Uptake Value
TOF	Time-of-Flight
TSH	Thyroid stimulating hormone

Table of contents

1. Introduction.....	4
2. Study design.....	4
2.1 Sample size planning.....	5
3. Aims and objectives.....	6
4. Outcomes.....	6
4.1 Primary outcome.....	6
4.2 Secondary outcome.....	6
5. Population to be analyzed.....	6
6. Analyses.....	6
6.1. Primary outcome.....	6
6.2 Secondary outcome.....	7

1. Introduction

[figure not shown]
The study aims to improve the differentiation between malignant and benign lesions in the pancreas in patients with suspected pancreatic cancer by images 30min und 90min p.i. and a diagnostic CT of the abdomen with contrast medium in the context of TOF-18F-FDG PET/CT and thus to improve the quality of PET/CT findings. Also, a cut-off value of SUV (primary outcome measure) will be determined in correlation with the histopathological results to better differentiate between malignant and benign lesions of the pancreas. Secondary outcome measures are the better demarcation of pancreatic lesions of the adjacent anatomical structures as well as the tumor size.

2. Study design

Study subjects will be recruited from the patients with suspected pancreatic cancer who are referred to the Division of Nuclear Medicine for diagnostic staging using 18F-FDG PET/CT. As part of the preparation of the patients for the PET/CT examination, [name] and other staff members will provide the information, and in case of participation at the study, the Informed Consent (enclosed) will be signed. Patients had to be sober and should have a plasma glucose level < 140 mg/dl. Furthermore, the creatinine level < 1.2 mg/dl (for values >1.2 mg/dl no administration of contrast medium) and TSH level (for values <0.1 µU/ml no administration of contrast medium) will be checked.

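### The SUVmax cut-off is chosen and assessed in the same patients, with no stated selection rule and no correction for optimism

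*SAP*

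**What the plan says.** SAP 6.1 plans three things that bear on this point:

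- It opens with an ROC comparison: "The primary analysis will compare the SUVmax values of all detected pancreatic lesions", at both time points and for both reconstructions, with AUCs compared by the DeLong test.
- It then plans "Sensitivity and specificity of SUVmax of each imaging modality (with and without TOF"), judged against histopathology. No threshold is given.
- It adds that "a cut-off value of SUVmax for differentiating malignant and benign pancreatic lesions will be computed using ROC-analysis". No criterion is given.

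SAP section 5 says "There is only one population in this clinical trial". Neither document mentions a hold-out set, an external set, resampling or a numeric SUV threshold. The Protocol's background rule on early and delayed uptake is qualitative and supplies no cut-off.

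The cut-off is not a side product. SAP section 1 says "a cut-off value of SUV (primary outcome measure) will be determined in correlation with the histopathological results", and the Protocol's aim includes it. SAP 4.1, however, lists SUVmax itself as the primary outcome.

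**The concern.** A rule such as the Youden index picks the threshold at which the observed sensitivity and specificity look best together. Part of that good appearance is chance in the particular sample. If accuracy is then read off at that threshold in the same lesions, the chance part is counted as performance. The effect is larger for specificity because benign cases are the minority, so the observed specificity curve is the noisier of the two.

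A published cut-off is used together with the sensitivity and specificity printed beside it. If those are optimistic, later users will expect fewer false positives than they will see. Because the rule is not named, readers cannot judge how far to discount the figures, and the rule could be picked after the curves have been seen.

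**Working it through.** **Inputs from the documents.** N is 118 and SAP 2.1 plans "at a prevalence of malignant lesions of 70% (corresponding to 30% benign lesions"). The Protocol's background section gives "benign diseases with a frequency of 19-34" per cent.

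- 118 × 0.30 = 35.4, so 35 benign and 83 malignant.
- 118 × 0.19 = 22.4, so 22 and 96.
- 118 × 0.34 = 40.1, so 40 and 78.

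**The plan's own figure.** SAP 2.1 asks that the 95% confidence interval around an expected specificity of 70% exclude 45%, with 90% power:

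n(benign) = (1.960 + 1.282)² × 0.70 × 0.30 / 0.25² = 35.3, and 35.3 / 0.30 = 117.7, rounded up to 118.

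The stated size reproduces. The formula treats specificity as a proportion at a threshold fixed in advance.

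**Assumptions not in the documents.** SUVmax is binormal, true AUC is 0.60 to 0.85, the malignant SD is 1.0 or 1.5 times the benign SD, and each patient has one lesion. The last is a simplification, since SAP 6.1 analyses all detected lesions.

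**Method.** Benign values are N(0, 1) and malignant values N(μ, σ²), with μ = Φ⁻¹(AUC) × √(1 + σ²). In each simulated trial the rule chooses a cut-off c. Apparent specificity is the share of that trial's benign values below c; true specificity is Φ(c). Optimism is the mean of apparent minus true. Sensitivity is handled in the same way, with true value Φ((μ − c)/σ). There were 6,000 trials per setting (4,000 for the benign-range runs).

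**Control.** With a cut-off fixed in advance at AUC 0.75 and equal SDs, mean observed specificity was 68.3% against a true 68.3%: no bias.

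**Optimism at 35 benign and 83 malignant, in percentage points:**

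| Rule | Specificity | Sensitivity |
|---|---|---|
| Youden | 5.0–7.5 | 2.2–3.3 |
| Closest to corner | 4.1–5.2 | 1.7–2.2 |
| Sensitivity fixed at 90% | 0–3 | about 1 |

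In the last row, the specificity figure depends on where the threshold sits: about 0 at the malignant value itself, 0.5–0.9 at the midpoint between neighbours, and 2.0–2.8 just above the last benign value.

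**Example at AUC 0.75, equal SDs, apparent against true specificity:**

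- Youden: 72.8 − 66.6 = 6.2 points.
- Corner: 71.5 − 66.9 = 4.6 points.
- Fixed 90% sensitivity (midpoint): 37.9 − 37.3 = 0.6 points.

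**Specificity optimism over the Protocol's benign range:**

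| Benign cases | Youden | Corner |
|---|---|---|
| 22 | 7.0–10.6 | 5.8–7.5 |
| 40 | 4.5–6.8 | 3.7–4.8 |

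**Independent repeat.** A separate run of 10,000 trials per setting (equal SDs, 35/83, AUC 0.65 to 0.90) gave specificity optimism falling from 7.2 to 4.8 points for Youden and from 5.1 to 3.8 for corner. At AUC 0.75, apparent specificity exceeded true specificity in 82% of trials under Youden and 73% under corner.

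**Does the remedy work?** Five repeats of stratified 10-fold cross-validation, with the cut-off re-selected in every fold (1,000 trials per setting), left a mean bias in specificity of −0.9 to +0.9 points (Youden), −0.5 to +0.4 (corner) and −0.9 to +0.3 (fixed 90%), and in sensitivity of −0.6 to +0.7.

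**The case against.** The strongest reply is that the link is inferred. SAP 6.1 mentions the SUVmax sensitivity and specificity before the cut-off and never says that one is taken at the other. That is true, and the concern is conditional for this reason. But no other threshold exists in either document, so the alternative reading is that the accuracy figures have no defined threshold at all.

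Second, the size rests on an AUC, a distribution and a rule that the documents do not give, and with a fixed sensitivity the bias could be negligible. This stands. It is why the size is shown as a range, and it is also an argument for naming the rule.

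Third, the optimism enters both reconstructions and largely cancels between them. In a paired simulation (Youden, 35/83, equal SDs, assumed correlation 0.90 to 0.95), net optimism in the TOF minus non-TOF specificity difference was about 0 with equal AUCs and about −1 point at 0.70 against 0.80. This stands too: the concern is with the absolute values reported beside the cut-off.

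Fourth, sampling error is at least as large: √(0.7 × 0.3 / 35) = 0.077, or 7.7 points for specificity near 70%. That is correct, but an optimism of 4 to 8 points is a systematic shift that an ordinary interval around the apparent value does not show.

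**Conclusion.** The concern holds. The SAP derives the SUVmax cut-off by ROC on its only population, without a named criterion or an optimism correction. If the SUVmax sensitivity and specificity are taken at that cut-off, they will on average be optimistic under common rules. Under the stated model with 35 benign and 83 malignant cases, the overstatement of specificity is about 4 to 8 points for Youden or closest-to-corner; across 22 to 40 benign cases it is 3.7 to 10.6. With a fixed 90% sensitivity it is small.

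Three things are not affected or not claimed:

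- The DeLong comparison uses no cut-off.
- The accuracy of the PET/CT findings is untouched if those are reader judgements.
- SAP 2.1 aims to show that "the specificity of the new method is higher than the old one" but does not say whether that method is SUVmax at this cut-off or the PET/CT findings, so no effect on the powered comparison is asserted.

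This is a moderate and predictable bias in a result that SAP section 1 treats as primary. It should be fixed, but it does not undermine the trial.

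**What to change.** Amend SAP 6.1 as follows:

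1. State that the SUVmax sensitivity and specificity are taken at the derived cut-off. Name one selection criterion, including where the threshold is placed between observed values, before SUVmax is linked to histology. Any target sensitivity is for the investigators to choose.
2. Report sensitivity and specificity from repeated stratified 10-fold cross-validation that repeats the cut-off selection, and any choice of time point or reconstruction, in every fold. Split by patient if patients have several lesions. Another internal correction that repeats the selection could serve; this one is suggested because its remaining bias was checked.
3. Label uncorrected values as *apparent* and state that the cut-off needs external validation.
4. If an interval is given, use a bootstrap that repeats the selection and is shifted for optimism or re-centred on the cross-validated value, and call it approximate. A plain percentile bootstrap is unsuitable: at AUC 0.75 under Youden with equal SDs its mean specificity was 74.5%, against 72.3% apparent and 66.3% true, and its coverage at nominal 95% was 85–90% (Youden) and 81–86% (corner) over the settings run. The shifted version gave 89–95% and 86–91%; the re-centred version gave 87–97% and 87–93%.

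The cost is SAP wording and a short script in R, which the SAP already names; no extra patients or readings are needed. At 35/83 the reported specificity will fall by about 5 to 8 points under Youden or 4 to 5 under corner, and sensitivity by about 2 to 3 or 2. Any interval for specificity will be wide: 26 to 64 points for Youden and 23 to 37 for corner in the simulations. Internal correction does not replace validation in new patients.
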